8.8 Retrieval and/or destruction of Investigational Product

All partially used or unused treatments will be retrieved by the Sponsor. A detailed treatment log of the returned IP will be established with the Investigator (or the pharmacist) and countersigned by the Investigator and the Monitoring Team.

The Investigator will not destroy unused IP unless the Sponsor provides written authorization to the contrary.

A potential defect in the quality of IP may be subject to initiation by the Sponsor of a recall procedure. In this case, the Investigator will be responsible for promptly addressing any request made by the Sponsor, in order to recall IP and eliminate potential hazards.

8.9 Concomitant treatment

8.9.1 Prohibited concomitant treatment

- Anti-obesity drugs (eg, sibutramine, orlistat, phentermine, amphetamines, open-label cannabinoid receptor antagonists, or other drugs or herbal or over-the-counter medications for weight reduction)
- Thyroid preparations other than thyroxin replacement treatment.

8.9.2 Permitted concomitant treatment

Any drugs other than those listed above are allowed, and should be administered, as necessary for the treatment of the patient, when possible with a stable dose, at the discretion of the Investigator. Treatment for dyslipidemia, hypertension, and/or diabetes should be initiated as soon as the need for treatment is identified, in accordance with treatment guidelines provided and standard of care, and should be adjusted as necessary to treat the patient's condition(s). All treatment with these drugs should be recorded on the appropriate CRF.

8.10 Treatment compliance

Compliance is assessed by counting the number of returned tablets in each wallet card at each visit. The Investigator (or delegate) must complete the appropriate pages of the treatment log form and of the CRF. A discontinuation is defined as a period with a least five consecutive days without study drug intake.

The monitor supervising the study will verify the data by comparing the recorded data with the investigational product retrieved.

9. ASSESSMENT OF INVESTIGATIONAL PRODUCT

9.1 Efficacy

9.1.1 Efficacy criteria

9.1.1.1 Primary criterion

The first occurrence of any component of the following cluster, as adjudicated by the Clinical Events Committee:

- Any MI (nonfatal or fatal¹³)
- Any stroke (nonfatal or fatal¹³)
- Cardiovascular death

9.1.1.2 Secondary criterion

The first occurrence of any component of the following cluster:

- Any MI (nonfatal or fatal¹³)
- Any stroke (nonfatal or fatal¹³)
- Cardiovascular death, and
- Hospitalization for cardiovascular cause (unstable angina, transient ischemic attack, cardiac rhythm disorder, congestive heart failure, syncope, or urgent revascularization procedure)

9.1.1.3 Other criteria

All-cause mortality

¹³ The diagnosis of fatal MI or fatal stroke is based upon:

- either death occurring within 28 days of the onset of the acute MI or stroke, in the absence of other clear cause,
- or death occurring more than 28 days after the onset of the acute MI or stroke, if that is the best clinical judgment and/or the CEC judges MI or stroke to be the cause of death, as appropriate,
- or autopsy confirmation of an acute MI or stroke as cause of death.

The following events taken separately:

- Myocardial infarction (nonfatal or fatal¹³).
- Any stroke (nonfatal or fatal¹³/ischemic, hemorrhagic or of uncertain type).
- Cardiovascular death
- Hospitalization for unstable angina, transient ischemic attack, cardiac rhythm disorder, congestive heart failure, syncope, or urgent revascularization procedure.

9.1.2 Clinical assessment methods

9.1.2.1 Definitions of components of the primary efficacy endpoint:

9.1.2.1.1 Myocardial infarction (MI)

Based on American College of Cardiology (ACC) Definitions for Measuring Outcomes (33), three main situations will be considered:

1. Patient who did not undergo recent cardiac intervention (within prior 24 hours):
At least one of the following must be present (biomarker assay must be performed):
 - a) CK-MB elevation ($>2xULN$ in one sample or $>ULN$ in two samples)
 - b) Troponin elevation ($>ULN$ in one sample)
 - c) CK elevation (in absence of a and b, $CK >2xULN$)

AND

At least one of the following (ECG must be performed and documentation should be provided to the Clinical Events Committee):

- Ischemic symptoms within last 24 hours
 - ST depression of at least 0.1 mV or T wave inversion
 - LBBB (new or old) or paced rhythm that obscures assessment of ST
 - ST elevation (new ST elevation in at least two contiguous leads ≥ 0.2 mV in V1, V2, or V3 or ≥ 0.1 mV in other leads)
 - New tall R wave with $R/S \geq 1$ in V1 and $R/S \geq 1.5$ in V2
 - New Q waves ≥ 40 ms in two contiguous leads
2. Patient who underwent recent PCI/CABG (within prior 24 hours):
 - a. Percutaneous coronary intervention (PCI): CK-MB $\geq 3xULN$ (no ECG changes or symptoms required)
 - b. Coronary artery bypass graft (CABG): either CK-MB $\geq 5xULN$ and new Q-waves, as defined above, or CK-MB $\geq 10xULN$ (with or without Q-waves)
 3. If new Q-waves ≥ 40 ms in two contiguous leads occur in a diabetic patient, an MI diagnosis will be established even in the absence of ischemic symptoms and enzyme elevations.

MIIs will be subsequently categorized as Q-wave MI or non Q-wave MI.

All appropriate supportive documentation should be provided to the Clinical Events Committee (see [Appendix 4](#)).

9.1.2.1.2 Stroke

Defined as an acute neurological vascular event with focal signs lasting more than 24 hours, with or without evidence of primary intracranial hemorrhage (PICH). Strokes will be further categorized as ischemic, hemorrhagic, or uncertain type.

If a previous deficit has worsened, it must have lasted more than one week, or more than 24 hours if accompanied by an appropriate new CT or MRI finding.

CT scan or MRI should be performed and should be provided in addition to other appropriate supportive documentation (see [Appendix 4](#)) to the CEC to allow further classification.

9.1.2.1.3 Cardiovascular death (CVD)

Defined as any death with a clear cardiac or vascular cause or unknown cause (including sudden death, unobserved and unanticipated death and other death not definitely attributed to a non-vascular cause). Only death due to a documented non-cardiovascular cause will be classified as non-cardiovascular. Death due to hemorrhage, other than PICH, and to pulmonary embolism will not be considered as a cardiovascular death.

Supportive documentation should be provided to the Clinical Events Committee for classification of cause of death (see [Appendix 4](#)).

9.1.2.2 Definitions of secondary efficacy endpoints:

9.1.2.2.1 Hospitalization

Defined as an overnight hospital stay, except for TIA, where treatment in an Emergency Department without hospital admission is acceptable, provided that the diagnosis of TIA is confirmed.

9.1.2.2.2 Transient ischemic attack (TIA)

Defined as a focal ischemic neurological deficit (cerebral or retinal), considered to be of ischemic origin, with a neurological deficit persisting less than 24 hours. As for stroke, CT scan or MRI should be performed to confirm the ischemic nature of the event.

9.1.2.2.3 Unstable angina (UA)

Defined as the onset of characteristic ischemic chest pain in the precordium or associated referral areas (occurring at rest or with minimal exercise, lasting longer than 5 minutes or requiring sublingual nitroglycerin for the relief of the pain), documented by ECG changes compatible with ischemia [e.g. ST depression (at least 1 mm in two contiguous leads), T-

wave inversion (at least 2 mm in two contiguous leads), or hyperacute peaked T waves, or new normalization of T waves], in the absence of fulfillment of the non-fatal MI definition.

9.1.2.2.4 Urgent revascularization procedure

Defined as any of the following procedures:

- Coronary revascularization: PCI (includes PTCA, coronary stenting, and others such as brachytherapy, atherectomy, laser, and rotational ablation) or CABG;
- Cerebrovascular revascularization: carotid endarterectomy, carotid percutaneous transluminal angioplasty (PTA with or without stent);
- Peripheral revascularization: peripheral arterial bypass surgery, PTA, or any therapeutic intervention for critical leg ischemia (including thrombolysis), or aortic aneurysm repair;

performed in an expedited fashion for worsening or unstable symptoms resulting in hospitalization.

9.1.2.2.5 Cardiac rhythm disorder

Defined as any abnormal cardiac rhythm, such as atrial fibrillation or ventricular arrhythmias and including any conduction abnormality, that is documented by ECG or Holter monitoring and requires an overnight hospital stay, prolongs hospitalization, or requires cardioversion or device implantation.

9.1.2.2.6 Congestive heart failure

Defined as inadequate cardiac output, as manifested by symptoms, such as dyspnea and/or orthopnea, and objective signs, such as peripheral edema, rales, jugular venous distension, arterial oxygen desaturation, and/or pulmonary edema on chest X-ray, found to be of cardiac cause.

9.1.2.2.7 Syncope

Defined as loss of consciousness that requires hospitalization for diagnosis and/or treatment.

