10.3 Waiver

Expected cardiovascular efficacy endpoints specified in this trial (primary and secondary efficacy criteria) will not be considered as AEs and will not be subject to expedited regulatory reporting. They will be reported on specific outcome event forms, which should be sent within one (1) working day, by FAX, to the Central Database number.

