13.7.1.2.4 Multiple comparisons/multiplicity

If the primary efficacy reaches statistical significance, then the two secondary endpoints will be formally tested at the 5% level in a hierarchical (step-down) procedure. First the MI, stroke, cardiovascular death or hospitalization endpoint will be tested, and then, if this reaches significance, the all-cause mortality endpoint will be tested.

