Appendix 4: The Clinical Events Committee (CEC)

Responsibilities

The Clinical Events Committee is charged with the responsibility for validating all reported primary efficacy outcomes and validating the classification of the cause of all deaths. The event adjudication process will be coordinated by C5.

Members of the Clinical Event Committee will be chosen based on their clinical expertise and language skills. It is expected that most languages will be represented by 2 cardiologists and 2 neurologists. Adjudicators will be trained at a preliminary meeting where study definitions will be reviewed and test cases performed to ensure uniform application of study definitions. Reported events will be adjudicated by at least one committee member. Dossiers of reported events will be prepared and distributed to committee members on a regular basis to ensure that events are adjudicated in a timely fashion. Each committee member will be requested to review the dossiers sent to him/her and acknowledge in writing his/her agreement/disagreement with the investigator's interpretation of events.

Definitions for Validation of Reported Outcome Events

Reported outcome events are all defined in the protocol and only these definitions should be used for adjudication.

- Adjudication of strokes will rely on neurologists in charge of validating such events and their classification as ischemic strokes (IS), hemorrhagic strokes or strokes of unknown cause. Hemorrhagic strokes will be further classified as PICHs and non-PICHs by a Central Neurologist.
- Adjudication of myocardial infarctions (MI) will rely on cardiologists in charge of validating such events and their classification as Q wave MI or non-Q wave MI.
- Adjudication of the cause of death will be performed by the following:
 - neurologists for validation of suspected fatal strokes.
 - cardiologists for all other deaths classified as fatal MI, other CVD, or non-CVD

Fatal strokes, fatal MIs, and other cardiovascular deaths (including unknown causes) will constitute cardiovascular deaths.

Review process for reported efficacy outcome events

- First adjudicator agrees with Investigator's report of outcome event:
 - Agreement acknowledged in writing and filed at C5
 - Event Adjudication database updated accordingly
 - Investigator's report of outcome event accepted
 - Adjudication complete

- First adjudicator disagrees with Investigator's report of outcome event:
 - Disagreement or uncertainty acknowledged in writing

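### Syncope in the tested secondary endpoint needs no cardiovascular cause, which conflicts with the component's heading and leaves unclear which losses of consciousness Section 10.3 exempts from adverse-event reporting

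*Protocol*

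**What the plan says.** Protocol Section 9.1.1.2 names the extra component of the secondary composite as "Hospitalization for cardiovascular cause (unstable angina, transient ischemic attack, cardiac rhythm disorder, congestive heart failure, syncope, or urgent revascularization procedure"; Section 13.7.2.1 repeats it. Section 9.1.2.2.7 then defines syncope: "Defined as loss of consciousness that requires hospitalization for diagnosis and/or treatment". Nothing further is required. One section earlier, congestive heart failure must be "found to be of cardiac cause".

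Section 13.7.1.2.4 places the composite directly after the primary endpoint: "First the MI, stroke, cardiovascular death or hospitalization endpoint will be tested", at the 5% level, with all-cause mortality tested only if it succeeds.

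Appendix 4 charges the Clinical Events Committee (CEC) with "validating all reported primary efficacy outcomes" and with classifying causes of death. Section 6.4 likewise confines it to the primary outcomes. Secondary hospitalizations are not in its remit.

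Section 10.3 states: "Expected cardiovascular efficacy endpoints specified in this trial (primary and secondary efficacy criteria) will not be considered as AEs". It also exempts these events from expedited regulatory reporting and sends them to outcome event forms.

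On length of stay, Section 9.1.2.2.1 has hospitalization "Defined as an overnight hospital stay, except for TIA". Section 9.1.2.2.5 counts a rhythm disorder that "requires an overnight hospital stay, prolongs hospitalization, or requires cardioversion or device implantation".

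**The concern.** The heading limits the component to cardiovascular causes; the syncope definition does not. No committee is assigned to settle the difference, so each site must choose which text to follow. The choice affects two results.

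- **Efficacy.** A hospitalized loss of consciousness from a seizure or hypoglycemia meets the literal definition. Hypoglycemia is not remote, since type 2 diabetes is a qualifying condition in Section 7.2. Such events would enter the first test after the primary and, through it, bear on whether all-cause mortality is formally tested.
- **Safety.** An event taken as a secondary criterion is waived from AE status and expedited reporting, and so drops out of the AE and SAE summaries in Section 13.8.1. That sits badly with the rest of the protocol. Section 9.2 sets up scripted neurological questions, and Section 10.1 gives a convulsion without hospitalization as an example of a medically important event. On the literal text, a convulsion managed at home may be an SAE, while one leading to an overnight stay with loss of consciousness may become a waived efficacy event. Section 4.2 describes the drug's target receptors as partly central.

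The rhythm-disorder mismatch is a smaller, separate point. A same-day cardioversion or device implantation counts under one section and fails the overnight-stay rule of the other.

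**Working it through.** **1. Cause required by each component definition (Section 9.1.2.2)**

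| Component | Cardiovascular criterion in its definition |
|---|---|
| Transient ischemic attack | Ischemic origin |
| Unstable angina | Ischemic pain with ECG changes |
| Urgent revascularization | Listed vascular procedures |
| Rhythm disorder | Abnormal rhythm on ECG or Holter |
| Congestive heart failure | Cardiac cause |
| Syncope | None |

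Syncope is the only one without a cardiovascular criterion.

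**2. A hospitalized seizure followed through the text**

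- Section 9.1.2.2.7 alone: loss of consciousness with hospitalization, so it qualifies.
- Heading in Sections 9.1.1.2 and 13.7.2.1: not a cardiovascular cause, so it does not qualify.
- CEC: no stated role for this component, so the conflict stays with the investigator.
- Section 10.3: if it qualifies, it is not an AE and goes on an outcome form. If not, it is an AE, and serious because of the hospitalization.
- Section 13.8.1: the summaries cover AEs and SAEs, so the event appears only on the second reading.
- Section 6.4 and Appendix 5: on the first reading it still reaches the Data Monitoring Committee (DMC), because outcome events are part of its data and it reviews all reported ones, summarized apart from AEs.

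**3. Overnight stay**

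Section 9.1.2.2.1 makes transient ischemic attack the only exception. Section 9.1.2.2.5 joins cardioversion and device implantation to the overnight stay with *or*. Both cannot hold for a same-day procedure.

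**4. Size of any dilution (illustration)**

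Inputs from Section 13.2: 15% risk reduction (HR 0.85), two-sided 5%, power 90%, approximately 1,600 events, all for the primary endpoint. Assumptions: the same HR on the genuine secondary components, a share q of control-arm events that are non-cardiovascular, and HR 1.0 for those events. The documents do not give q or the number of secondary events.

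Plan's figure first (Schoenfeld): events = 4(1.960 + 1.282)² / (ln 0.85)² = 1,592. Freedman's formula gives 1,599. Power at 1,600 events is 90.2%. The stated figure reproduces.

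Diluted HR = 0.85(1 − q) + 1.0q = 0.85 + 0.15q.

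- q = 5%: HR 0.8575; (ln 0.85 / ln 0.8575)² = 1.12, about 12% more events for equal power.
- q = 10%: HR 0.865; (ln 0.85 / ln 0.865)² = 1.26, about 26% more events.

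| q | HR | Power, 1,600 events | Power, 2,400 events (assumed) |
|---|---|---|---|
| 0 | 0.85 | 90.2% | 97.8% |
| 1% | 0.8515 | 89.5% | 97.6% |
| 5% | 0.8575 | 86.8% | 96.5% |
| 10% | 0.865 | 82.7% | 94.4% |

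If the drug itself raised such events (HR 1.5, purely assumed), q = 5% gives 0.95 × 0.85 + 0.05 × 1.5 = 0.8825, with power 70.5% at 1,600 events and 86.5% at 2,400.

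**The case against.** The best defence is that Section 9.1.2.2.7 should not be read alone. Syncope is nested under a cardiovascular heading wherever the component is listed, and Section 10.3 speaks of expected cardiovascular endpoints. Section 10.1 asks that symptoms be grouped under a diagnosis, so a diagnosed seizure would be recorded as a seizure. A cause-free definition also spares sites a subjective attribution, and noise unrelated to treatment pulls the result towards no effect.

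Much of this stands, and it rules out several stronger readings that a reader might infer:

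- *The protocol orders non-cardiovascular events to be scored as efficacy.* It does not. The texts conflict, and the narrower reading has support.
- *These events leave the safety data.* They leave the AE and SAE summaries and expedited reporting. Outcome forms and the DMC's data still carry them.
- *Outcome reports that the CEC rejects disappear from every table.* The protocol does not say so. It promises written adjudication guidelines, and syncope is not adjudicated in any case, so no count of lost reports can be drawn from the documents.
- *The secondary test is materially weakened.* This is not shown. Section 13.2 sets no power target for it, and the composite contains all the primary event types plus hospitalizations.

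The defence does not remove the conflict. The grouping rule governs how AEs are written down, not which events meet an outcome definition. If a cause-free definition was intended, the heading and the waiver no longer fit it.

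**Conclusion.** The point holds as an internal inconsistency with consequences for classification. The literal syncope definition admits non-cardiovascular loss of consciousness into an unadjudicated component of the first endpoint tested after the primary, and the waiver can then keep those events out of the Section 13.8 AE and SAE summaries. Sections 9.1.2.2.1 and 9.1.2.2.5 contradict each other on the overnight stay.

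The number of events affected cannot be derived from the documents. Under the stated assumptions, a 5% or 10% unrelated share would need about 12% or 26% more events for equal power; with a larger secondary event count the loss of power is only a few percentage points. Power is therefore the lesser issue, and classification and safety tabulation the main one. The primary endpoint and its sample size are unaffected. The correction should be made.

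**What to change.** 1. In Section 9.1.2.2.7, require a presumed cardiac or vascular cause, or a cause unexplained after work-up, so that the definition matches the component heading.
2. In Section 10.3, state that loss of consciousness attributed to a non-cardiovascular cause is not covered by the waiver and is reported and tabulated as an AE or SAE.
3. Reconcile Sections 9.1.2.2.1 and 9.1.2.2.5 on whether a rhythm disorder treated by cardioversion or device implantation counts without an overnight stay.

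The cost is amended endpoint wording and outcome-form instructions, slightly fewer secondary events and some added SAE processing. The sample size and primary analysis do not change.

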9.1.2.3 Definition of other efficacy endpoint

9.1.2.3.1 Non-cardiovascular death (non-CVD)

Defined as any death with documented non-cardiovascular cause.

9.2 Safety

Safety evaluation will rely on capturing all AEs reported (including neurological and psychiatric AEs based on clinically relevant results of scripted questions asked at each follow-up visit and phone call and on physical examination findings), on vital signs

(supine heart rate and blood pressure) obtained at one, three and six month visits, then at every 6-month visit and at the final visit, and on physical examination and hematology (Hb, Ht, WBC-diff, platelets), and biochemistry (ALT, AST, ALP, creatinine) values obtained at 6-month visits and at the final visit.

10. PATIENT SAFETY

10.1 Adverse Events monitoring

Definitions:

An adverse event is any untoward medical occurrence in a clinical investigation patient administered a pharmaceutical product and which does not necessarily have to have a causal relationship with this treatment.

A Serious Adverse Event is any untoward medical occurrence at any dose that:

- Results in death or;
- Is life-threatening or;

Note: The term "life-threatening" in the definition of "serious" refers to an event in which the patient was at risk of death at the time of the event; it does not refer to an event that hypothetically might have caused death if it were more severe.

- Requires inpatient hospitalization or prolongation of existing hospitalization or;
- Results in persistent or significant disability/incapacity or;
- Is a congenital anomaly/birth defect;
- Is a medically important event:

Medical and scientific judgment should be exercised in deciding whether expedited reporting is appropriate in other situations, such as important medical events that may not be immediately life-threatening or result in death or hospitalization but may jeopardize the patient or may require intervention to prevent one of the other outcomes listed in the definition above. These should also usually be considered serious.

Note: Examples of such events are intensive treatment in an emergency room or at home for allergic bronchospasm, blood dyscrasias, convulsions or asymptomatic ALT increase greater than 10x ULN that does not result in hospitalization, or development of drug dependency or drug abuse.

Adverse Events

All Adverse Events regardless of seriousness or relationship to Investigational Product, including those from the first visit planned in the Clinical Trial Protocol/signature of the informed consent form, are to be recorded on the corresponding page(s) included in the

Case Report Form. Whenever possible, symptoms should be grouped as a single syndrome or diagnosis. The Investigator should specify the date of onset, intensity, action taken with respect to Investigational Product, corrective treatment/therapy given, outcome and his/her opinion as to whether there is a reasonable possibility that the Adverse Event was caused by the Investigational Product.

Lab, vital signs, or ECG abnormalities are to be recorded as adverse events only if they are medically relevant: symptomatic, require corrective treatment, lead to study drug discontinuation and/or fulfill a seriousness criterion.

Serious Adverse Events

In the case of a Serious Adverse Event the Investigator must immediately:

- SEND (within 1 working day, by fax) the signed and dated corresponding page(s) in the Case Report Form to the representative of the Monitoring Team whose name, address and fax number appear on the Clinical Trial Protocol, or to a designated Safety fax number provided by the Monitoring Team, as well as to the Central Database number;
- ATTACH a photocopy of all examinations carried out and the dates on which these examinations were performed. Care should be taken to ensure that the patient's identity is protected and the patient's identifiers in the Clinical Trial are properly documented on all copies of source documents provided to the Sponsor. For laboratory results, include the laboratory normal ranges;
- Follow-up of any Serious Adverse Event that is fatal or life threatening should be provided within one additional calendar week. The treatment code will be unblinded for reporting of Serious Adverse Events that are unexpected and reasonably associated with the use of the Investigational Product.

Follow-up

- The Investigator should take all appropriate measures to ensure the safety of the patients, including referral to a specialist if indicated. Notably he/she should follow up the outcome of any adverse events (clinical signs, laboratory values or other, etc) until the return to normal or stabilization of the patient's condition;
- In the case of any serious adverse event, the patient must be followed up until clinical recovery is complete and laboratory results have returned to normal, or until progression has been stabilized. This implies that follow-up may continue after the patient has left the Clinical Trial and that additional investigations may be requested by the Monitoring Team;
- In case of any serious adverse event brought to the attention of the Investigator at any time after cessation of Investigational Product and considered by him/her to be caused by the Investigational Product with a reasonable possibility, this should be reported to the Monitoring Team.

